9 INVESTIGATIONAL PLAN

9.1 Overall Study Design and Plan-Description

The clinical trial is designed as an investigator-initiated, prospective, randomized, open, blinded endpoint assessment (PROBE) interventional multi-center phase 4 trial to assess safety, tolerability, and efficacy of standard APP therapy in patients with AHRF due to pneumonia, and to evaluate if a standard APP therapy strategy is superior to standard supine/semi-recumbent positioning therapy in reduction of mortality and tracheal intubation endpoints in patients with AHRF. The trial has an adaptive design with an interim analysis and re-calculation of the sample size after follow-up of 50% of the planned sample size has been recruited.

APP will be carried out according to the proning strategy described in the study manual. The control group will receive standardized supine positioning therapy. The clinical trial will be conducted in an outcome assessor-blinded manner.

9.2 Discussion of Study Design, Including the Choice of Control Groups

So far, PP has shown a reduction in mortality in mechanically ventilated patients with moderate to severe ARDS. However, to date it remains unclear if PP in spontaneous breathing patients with AHRF and need for oxygen supplementation or non-invasive mechanical ventilation methods also benefit from so called awake prone positioning trial. Whether or not standard APP improves prognostic relevant parameters is unclear. Therefore, this trial is of utmost importance.

To this end a standard APP therapy strategy will be compared with a standard supine/semi-recumbent positioning therapy strategy in a clinical trial setting. This is scientifically the strongest possible design and ethically appropriate given the limited evidence for therapeutic options in AHRF.

9.3 Selection of Study Population

Since morbidity and mortality in AHRF patients is high, effective therapies are needed to further improve outcome and quality of life are needed. A therapy which is only symptomatic or based on expert consensus is considered to be not fully sufficient. The improvement of prognostic relevant endpoints through a well-tolerated therapy with the potential to also improve quality of life is regarded the ultimate goal.

9.3.1 Inclusion Criteria

The focus of this trial is to treat patients with respiratory failure. The inclusion criteria are selected accordingly. Patients meeting all of the criteria listed below will be included in the study:

- Patients in the intensive care unit
- High possibility of Pneumonia (community-acquired pneumonia or hospital-acquired pneumonia) either diagnosed by chest x-ray or computed tomography or clinically diagnosed at least with one of the following signs
 - Appearance of purulent secretions or changes in characteristics (color, odor, quantity, consistency)
 - Cough or dyspnea or tachypnea
 - Evocative auscultation
- Presence of acute hypoxemic respiratory failure ($\text{PaO}_2/\text{FiO}_2 \leq 300 \text{ mmHg}$ or $\text{SpO}_2/\text{FiO}_2 \leq 315$)
 - with need for supplementary oxygen via HFNO, NIV or CPAP with at least 40% FiO_2

9.3.2 Exclusion Criteria

Patients are excluded from the study if any of the following criteria are met at screening or before randomization, a detailed list is shown in the study manual:

- Age below 18
- Pregnant woman
- Patient is unlikely/unable to awake prone positioning, or to be compliant as indicated by the treating team
- Prolonged need (≥ 4 days) for HFNO, NIV or CPAP before study inclusion
- Urgent need for endotracheal intubation
- Invasive Mechanical Ventilation
- Shock
 - Defined as need for vasopressor $\geq 0.4 \text{ mcg/kg/min}$ to maintain a mean blood pressure of $\geq 65 \text{ mmHg}$ or systolic blood pressure $\geq 90 \text{ mmHg}$
- Participation in another clinical interventional trial in the last 3 months
- Previous Participation in the PROSA Trial
- Long-term oxygenation therapy (LTOT) or continuous positive airway pressure (CPAP) therapy before hospital admission
- Treatment with intention of palliative care and/or Do not intubate order (DNI) at time of randomization

9.3.3 Removal of Patients from Therapy or Assessment

The study in its entirety may be discontinued prematurely by the Coordinating Investigator or Sponsor at any time (see below), and/or individual patients may terminate their participation prematurely, or have their participation be terminated by an Investigator.

9.3.3.1 Temporarily Treatment Discontinuation

Treatment may be interrupted, if this is deemed necessary by the treating physician. This might be the case when clinically relevant side effects occur.

Restarting of therapy is allowed and encouraged, but fully lies at the discretion of the investigator.

9.3.3.2 Premature Treatment Discontinuation

Physicians must stop treatment if the patient experiences any kind of relevant side effect. The patient may remain in the study and continue to attend study visits.

APP will be discontinued when the patients meet criteria for endotracheal intubation or the patients develops other criteria as defined in the study manual.

9.3.3.3 Withdrawal of Patients from the Study

The following circumstances may lead to discontinuation of the study by an individual patient who will then be recorded as a drop-out. They include, but are not limited to the following issues:

- Withdrawal for personal reasons
- Adverse events necessitating withdrawal from the study
- Circumstances in which the health of the patient would be endangered upon continued participation in the study
- Lost-to follow-up

If a patient withdraws from the study at any time either at his or her request or at the Investigator's discretion, an "End-of-Study" visit should be performed and the "End-of-Study" eCRF section should be used to collect the relevant information. For the "End-of-Study" visit the same assessments should be made as for the discharge visit. The reason(s) for withdrawal must be recorded on the relevant page of the patient's eCRF and the patient's source data.

It is vital to obtain follow-up data for any patient withdrawn from the study because of an AE. Every effort must be made to undertake protocol-specific safety follow-up procedures. If a patient is discontinued due to an AE, the event should be followed up until resolution or until the event becomes chronic.

If a patient refuses to continue study procedures, the reason for refusal should be fully documented in the patient's source document and recorded in the study-specific eCRF.

It is the patient's right to withdraw from the trial without providing a reason. In this case, the source documents and the eCRF should document the reason for discontinuation as "withdrawal of consent".

9.3.3.4 Criteria for Termination of the Study

The PROSA trial will be supervised by its Steering Committee and an independent Data Safety Monitoring Board (DSMB). All final decisions, however, regarding study termination or modification will be agreed with the Steering Committee and the independent DSMB.

No formal stopping rules will be set. An independent DSMB will monitor safety in the trial. Should safety concerns evolve, they should recommend stopping the study. Stopping the trial for efficacy or futility is an option.

9.3.3.5 Study Termination

Individual study completion is defined as patients having finished the treatment period without early termination and reached the last visit within the specified window per the Flow Chart (28 days).

Overall End of Study is defined as the date of last patient last visit (LPLV). Within 28 days after the End of Study the Coordinating Investigator and the Sponsor must inform regulatory authorities and ethics committees about the completion of the trial.

The Coordinating Investigator and Sponsor may terminate the trial at any time if serious safety concerns rise for the patients. In the case of study termination, participating sites will be informed of the procedures to be followed to ensure that adequate consideration is given to the protection of the patient's safety.

The Coordinating Investigator will be responsible for informing the Sponsor of the trial's termination within 24 hours. The Sponsor has to inform the Competent Authorities and the Ethics Committee within 15 days.

9.4 Interventional treatment

9.4.1 Study intervention

9.4.1.1 Clinical Intervention

The clinical intervention in the Intervention Group is Awake Prone Positioning, a standard therapy in intensive care units worldwide in ARDS care. The intervention should not be started later than 24 hours after randomization. An earlier start, as soon as possible, after randomization is strongly recommended. In patients in the intervention group standard Awake Prone Positioning for at least 10 hours/day for a length of 72 hours should be applied. To reach the targeted 10 hours / day (per 24 hours), it is strongly

recommended to use blocks of a longer time period (e.g. multiple 3-5 hours blocks) within the 24 h period to reach the anticipated APP goal. It is recommended that the APP therapy within the targeted intervention for 10 hours/day (per 24 h period) is not interrupted for more than 2 hours till reaching the goal of 10 hours / day (per 24 hours). It is further strongly recommended that one APP session should last at least 3 hours. Time in prone position may be prolonged if the patient is comfortable. A detailed instruction for APP can be found in the study manual.

Awake prone positioning will continue daily until the end of the 72 hours intervention period or one of the following stopping criteria is met before:

- 1) the patient is intubated
- 2) the patient is discharged from the ICU.

If patients have to be tracheal intubated and mechanically ventilated treatment should follow current ARDS guidelines according to the local protocol. This includes PP in patients with mild to severe ARDS if $\text{PaO}_2/\text{FiO}_2$ is below 150 mmHg.

9.4.1.2 Control group

Patients randomized to the control arm will receive standard positioning at the discretion of the treating team but excluding APP. Control group patients will remain in their natural choice of position, which is anticipated to favour a supine, semi-recumbent position. The use of awake prone positioning as a so-called rescue intervention is discouraged in the control group and recorded as a protocol violation.

If patients have to be tracheal intubated and mechanically ventilated treatment should follow current ARDS guidelines. This includes PP in patients with mild to severe ARDS if $\text{PaO}_2/\text{FiO}_2$ is below 150 mmHg.

9.4.1.3 Patient Management

Criteria for endotracheal intubation and guidelines for patient management including invasive mechanical ventilation, fluid management, and sedation will be provided as recommendations within the study manual. The patient management will be up to the discretion of the treating physician team.

9.4.1.4 Follow-up per Patient:

Follow-up for all patients will be according to Table 1 until the last patient recruited has completed 4 weeks (i.e. 28-days) follow-up.

9.4.1.5 Duration of Intervention per Patient:

Interventional Treatment will be administered during the first 72h after randomization.

9.4.1.6 Patient Compliance

Compliance must be assessed by the PI, or an Investigator.

9.4.2 Method of Assigning Patients to Treatment Groups

Randomisation will be carried out centrally through a computer-generated sequence (e.g. randomizer.at). Eligible patients will be randomized 1:1 to standard intervention or standard control group. Randomization will be stratified by centre, age and mode of respiratory support at inclusion using block randomization for each stratum with varying block sizes concealed from the investigator to minimize selection bias. The approach of stratified randomisation helps to avoid potential imbalances between the groups that might affect outcome and bias results.

Concealment of randomization will be ensured at each center through a remote dedicated online randomization system.

9.4.3 Blinding

Study sites and patients are not blinded, blinding is not possible due to the nature of the awake prone positioning procedure. Assessors of outcome will be blinded.

9.4.4 Unblinding

The subject's treatment group will be disclosed to himself/ herself.

9.4.5 Prior and Concomitant Therapy

Prohibited therapy: None

Concomitant therapy: Any concomitant treatment given for any reason during the course of the study must be recorded on the eCRF and in the patient's medical records, including dosage, start and stop dates and reason for use.

9.4.6 Treatment Compliance

9.4.6.1 Admission to the Study

A patient will only be admitted to the study if all inclusion and none of the exclusion criteria are met.

9.4.6.2 Patient Identification

The PI of each site will keep a record relating the patient numbers and the names of all patient that have given their informed consent, to allow easy checking of data in patient files, when required. This record will also include the date of the patient's enrolment and completion, as well as patients who could not be included in the study for whatever reason.

9.5 Efficacy and Safety Variables

9.5.1 Efficacy and Safety Measurement Assessed and Flow Chart

Details regarding scheduled assessments and procedures to be conducted in this study are provided below. For detailed assessment of schedules refer to Table1.

9.5.2 Appropriateness of Measurements

9.5.2.1 Screening Procedures

Written, signed, and dated informed consent from the patient prior to the performance of any study related procedures must be obtained by an Investigator. Patients (or legal representatives) will first have ample time to read the patient information before an Investigator will start the information and informed consent process. If the patient is incapable of giving consent personally a legal representative will be informed about the study and can give consent representing the patient. Informed consent from the patient will be obtained as soon as the patient is capable again. If the patient does not agree he/she will be withdrawn from the study.

An Investigator will provide the patients (or legal representatives) with information of the study and explain the nature of the study point by point. During these verbal patient information process, patients (or legal representatives) have already the opportunity to ask questions. After that, the patients (or legal representatives) have the opportunity to individually ask questions in a one-to-one meeting with the Investigator. If the Investigator is convinced that the patient (or legal representatives) understands the nature and risks of the trial, and each patient (or legal representatives) had ample time for consideration and formulation of questions (which could also mean that the patients (or legal representatives) first discuss the decision with friends or family members), and if all questions are answered, the patient (or legal representatives) will ask to personally sign the informed consent form. A copy or a second original of the signed informed consent form must be given to the patients (or legal representatives) for their records.

Only an authorised and trained Investigator may decide on the eligibility of the patient.

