	
Effect size assumed for power calculation: The sample size and power calculation are based on previous knowledge, assuming a 28-day event rate of the combined endpoint in the control group of 50%, and a reduction to 35% in patients with the experimental intervention. To account for possible imprecision regarding the assumptions, an adaptive design was chosen with one interim analysis after follow-up of 50% of the planned number of patients, in order to allow stopping early for futility or efficacy and to re-estimate the sample size. Based on these assumptions and for an overall one-sided type-one error of 2.5% and statistical power of 80%, 171 patients per group (342 overall) are planned to be enrolled to prove superiority. The maximum sample size will be restricted to 513 patients.
 
Safety: Rates of adverse events and serious adverse events will be tabulated by treatment group, according to type of event and system organ class. Safety endpoints for the APP group will be analysed descriptively (event rates with two-sided 95% confidence intervals).
 
Secondary endpoint(s): Treatment effects will be calculated with two-sided 95% confidence intervals and are of descriptive nature only. Secondary outcomes will be analysed depending on the scale type, corresponding to the primary analysis. Percentage of patients meeting key safety endpoints, as well as assessment of adverse events.

Safety:	To be randomized into the trial: n = 342 To be analysed: n = 342 – intention to treat analysis Adaptive sample size: n = 342 - 513
Number of Patients	
Note: adaptive sample size (see below for details)
 
Note: recruitment will be competitively among sites (currently 20 sites planned)

Table 1. STUDY SCHEDULES

Phase of study	Screening & Randomisation	Visit 2	Visit 3
Point in time	Day 1	Day 1-3	Day 28 (± 3 days)
Informed Consent	✓		
I/E Criteria	✓		
Medical History & Demographics	✓		
Vital Signs	✓	✓	
Routine laboratory values (blood count)	✓	✓	
Routine blood gas values	✓	✓	
Parameters of oxygenation and oxygenation therapy (HFNO, NIV, CPAP)	✓	✓	
Start of Intervention (Prone Positioning) therapy	✓	✓	
Endpoints	✓	✓	✓

Figure 1. Trial Flow

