5.3 Patient Information and Informed Consent

An Investigator will explain to the patients (or legal representative) the nature, significance and implications of the study. He will explain all methods, rules of conduct and any restrictions which may apply. Possible effects and side effects will be discussed. Patients (or legal representatives) will be informed that they are free to withdraw from the study at any time, without giving any reason for doing so. They must be able to understand the full implications of their decision. Study participation will be in consent with the patient or legal representative.

All participants (or legal representatives) will sign an informed consent form as evidence of consent. The patient information sheet and the informed consent form of each participant will be filed in the Investigator Site File (ISF). A second original of the signed consent form and a copy of the information sheet will be handed to the patients after signature and before enrolment.

If a patient is unconscious and not able to be informed/ to provide informed consent and a legal representation status is not established/ available, the inclusion is at the discretion of the local investigator and can be performed under an emergency enrolment strategy. In this case the informed consent process has to be repeated as soon as the patient is awake or a legal representation has been established as deferred consent strategy.

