It should be emphasised that as little patients as possible should discontinue treatment (or change to the other treatment arm) and that all patients should be followed up and also documented after discontinuation of the treatment in order to record data required according to the intention-to-treat principle. All efforts will be made to avoid missing data and to collect outcome data for all patients randomized in the trial. In the primary analyses, a negligible number of drop-outs is expected. In case of substantial dropout multiple imputation will be applied in sensitivity analyses.

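### Withdrawing patients who refuse at re-consent leaves their day-28 outcome unsecured, and this loss depends on the outcome

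*Protocol*

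**What the plan says.** Two routes lead to randomisation without the patient's own consent. Under section 9.5.2.1 a legal representative may consent for a patient who cannot, and "Informed consent from the patient will be obtained as soon as the patient is capable again". If the patient then declines, "If the patient does not agree he/she will be withdrawn from the study". Section 5.3 adds emergency enrolment when no representative is available; there "the informed consent process has to be repeated as soon as the patient is awake or a legal representation has been established as deferred consent".

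Section 9.3.3.3 covers withdrawal as "discontinuation of the study by an individual patient who will then be recorded as a drop-out". It asks for an End-of-Study visit with the discharge-visit assessments. On later follow-up it is emphatic for one group only: "It is vital to obtain follow-up data for any patient withdrawn from the study because of an AE".

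The synopsis defines the full analysis set (FAS) as all randomised patients in their randomised arm and states "To be analysed: n = 342". Section 9.7.1.2.1.1 puts it more softly, as close to intention-to-treat as possible. Section 9.7.1.2.2.2 aims at outcome data for everyone randomised and expects negligible drop-out. Its instruction to keep following patients concerns those who stop treatment. For missing outcomes it offers one provision: "In case of substantial dropout multiple imputation will be applied in sensitivity analyses".

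**The concern.** The rule ends study participation, not merely the intervention, and nothing secures intubation and vital status from the refusal to day 28. These are the two components of the primary endpoint.

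The loss is not random. A patient who dies before regaining capacity cannot refuse in person, and one who is intubated and sedated is asked later or not at all. Those who can refuse have survived and recovered capacity, and they are mainly event-free at that moment. Missingness therefore depends on the primary outcome.

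Patients and sites also know the allocation when consent is sought (section 9.4.3), and only one arm is asked to lie prone for 10 hours a day (section 9.4.1.1). Refusal could therefore differ by arm, and the estimated treatment effect would then be biased.

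**Working it through.** **Plan's own figure.** Inputs from section 9.7.1.3: event rates 50% and 35%, one-sided 2.5%, power 80%. With pooled variance, n = [1.96·√(2·0.425·0.575) + 0.8416·√(0.25 + 0.2275)]² / 0.15² = 169.3 per arm. The inflation factor for two O'Brien-Fleming looks is 1.0078, giving 170.6, so 171 as stated. The unpooled variance that section 9.7.1.3 names gives 166.6 × 1.0078 = 167.9, so 168; the difference does not matter here. There is no allowance for drop-out.

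**Assumptions.** The protocol gives neither the share f enrolled without own consent nor the refusal rate r. I take f = 5%, 10% and 30%, and suppose that only event-free patients are lost.

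**Formulas.**
- Lost per arm = f · r · 171 · (1 − p), where p is the true event rate.
- Observed odds ratio = true odds ratio × (1 − f·r_control) / (1 − f·r_APP).
- Standard error of the log odds ratio = √(sum of reciprocals of the four cell counts); drift = |log OR| / SE.
- Power = P(Z1 > 2.797 or Z2 > 1.977), correlation √0.5, with the first look at half the information. These bounds correspond to the stated 0.0026 and 0.024. Sample-size re-estimation, futility stopping and covariates are ignored.

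**Full data.** OR = (0.35/0.65)/(0.50/0.50) = 0.538; power 79.5%.

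**Equal refusal.** The factor in the odds-ratio formula is 1, so OR stays 0.538. With 10% refusal in both arms and f = 30%, the observed rates are 50.8% and 35.7%.

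**Unequal refusal, 5% control and 20% APP, f = 30%.**
- Lost: 0.30·0.05·171·0.50 = 1.3 control and 0.30·0.20·171·0.65 = 6.7 APP.
- Observed rates: 85.5/169.7 = 50.4% and 59.85/164.3 = 36.4%.
- OR = 0.538 × 0.985/0.940 = 0.564.
- Drift = 0.572/0.223 = 2.56; power 72%.

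| f | Lost, control / APP | OR | Power |
|---|---|---|---|
| 0 | 0 / 0 | 0.538 | 79.5% |
| 5% | 0.2 / 1.1 | 0.543 | 78% |
| 10% | 0.4 / 2.2 | 0.547 | 77% |
| 30% | 1.3 / 6.7 | 0.564 | 72% |

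**No true effect (50% in both arms), f = 30%.** With 5% control and 20% APP refusal, one-sided error falls from 2.5% to 1.5%. With the pattern reversed (20% control, 5% APP) it rises to 4.0%.

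**The case against.** The strongest reply is that the protocol orders withdrawal, not deletion. No section removes recorded data or takes refusers out of the FAS, and section 9.3.3.3 requires a closing visit at which an earlier intubation could be recorded. Section 9.7.1.2.2.2 wants outcomes for everyone randomised. This stands against the reading that refusers' data are erased and that they necessarily leave the primary model; a reader might infer that, but the text does not say it. What remains is the period from refusal to day 28. The closing visit does not cover it, and the continued follow-up that the protocol describes is for patients who stop treatment.

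It is also too strong to say that only recovered, event-free survivors can be lost. Under section 5.3 a representative established later may be asked on behalf of a patient still without capacity. Survivors who were intubated can refuse once awake, and they have already had a primary event. If all refusers' data were deleted, 40% of events were deaths and the other survivors refused alike, the f = 30% scenario would give OR 0.549 and power 75.7% rather than 0.564 and 72%.

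The share f may be low, because section 9.3.2 excludes patients on invasive ventilation and those judged unlikely to comply with awake proning. This stands and limits the size. The protocol nevertheless provides two routes for patients who cannot consent.

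Finally, the consent form and the analysis plan are not at hand. The form may already ask about continued use of data. An analysis plan, however, cannot recover outcomes that patients were never asked to permit.

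**Conclusion.** The point holds as a gap in the protocol with a cheap remedy. The re-consent rule does not secure day-28 outcomes after a refusal, the loss depends on the outcome, and the protocol does not reconcile this with analysing all randomised patients.

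The effect is probably small. At f = 5% about 1.3 patients are lost in total and power falls by about one percentage point. At f = 30% it falls by about seven. These figures rest on assumed values of f, on a fourfold difference in refusal between arms and on losing only event-free patients. Equal refusal leaves the odds ratio unchanged.

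A reader might infer that the rule threatens the type I error. The documents give no reason to expect that. The burden of proning suggests more refusal in the APP arm, which is conservative under the null and costs power instead. Inflation needs more refusal in the control arm.

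**What to change.** In sections 5.3 and 9.5.2.1, and in the consent form if it does not already do so, replace plain withdrawal by a stepped choice at re-consent, as ethics and law permit:

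1. Stop the intervention and study contacts.
2. Allow use of the data recorded so far.
3. Allow day-28 intubation and vital status to be taken from the hospital record.

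Keep in the FAS everyone who permits 2 or 3. Where use of data is permitted, count an intubation before refusal as an event. Report full refusals by arm. Whatever their number, add a sensitivity analysis that counts full refusers first as event-free and then as events.

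The cost is an ethics amendment, a slightly longer re-consent talk and one short analysis, with no extra patients or procedures. Some patients will still refuse everything. The change should be in place before patients reach re-consent, because permissions not sought then are hard to obtain afterwards.
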